7.2.2. Assessment of Severity

Severity of adverse events is to be determined based on GSI Grading Scale for Severity of Adverse Events and Laboratory Abnormalities ([Appendix 4](#)). A distinction should be drawn between seriousness and severity of AEs. An AE that is assessed as Grade 4 (potentially life-threatening) should not be confused with an SAE. Severity is a category utilized for rating the intensity of an event: both AEs and SAEs can be assessed as Grade 4. An event is defined as “serious” when it meets one of the predefined outcomes described above in Section [7.1.2](#).

7.3. Investigator Requirements and Instructions for Reporting Adverse Events and Serious Adverse Events to Gilead

Requirements for collection prior to study drug initiation:

After informed consent, but prior to initiation of study medication, the following types of events should be reported on the case report form (CRF/eCRF): all SAEs and adverse events related to protocol-mandated procedures.

Adverse Events

Following initiation of study medication, collect all AEs, regardless of cause or relationship, until 30-days after last administration of study IMP must be reported to the CRF/eCRF database as instructed.

All AEs should be followed up until resolution or until the adverse event is stable, if possible. Gilead Sciences may request that certain AEs be followed beyond the protocol defined follow up period.

Serious Adverse Events

All SAEs, regardless of cause or relationship, that occurs after the subject first consents to participate in the study (ie, signing the informed consent) and throughout the duration of the study, including the protocol-required post treatment follow-up period, must be reported to the CRF/eCRF database and Gilead Drug Safety and Public Health (DSPH) as instructed. This also includes any SAEs resulting from protocol-associated procedures performed after informed consent is signed.

Any SAEs and deaths that occur after the post treatment follow-up visit but within 30-days of the last dose of study IMP, regardless of causality, should also be reported.

Investigators are not obligated to actively seek SAEs after the protocol defined follow up period; however, if the investigator learns of any SAEs that occur after study participation has concluded and the event is deemed relevant to the use of IMP, he/she should promptly document and report the event to Gilead DSPH.

- All AEs and SAEs will be recorded in the CRF/eCRF database within the timelines outlined in the CRF/eCRF completion guideline.

Electronic Serious Adverse Event (eSAE) Reporting Process

- Site personnel record all SAE data in the eCRF database and from there transmit the SAE information to Gilead DSPH within 24 hours of the investigator's knowledge of the event. Detailed instructions can be found in the eCRF completion guidelines.
- If for any reason it is not possible to record the SAE information electronically, ie, the eCRF database is not functioning, record the SAE on the paper serious adverse event reporting form and submit within 24 hours to:

Gilead DSPH:

Fax: PPD
Email: PPD

Medical Monitor:

PPD
Phone: PPD
Fax: PPD
Email: PPD

- As soon as it is possible to do so, any SAE reported via paper must be transcribed into the eCRF Database according to instructions in the eCRF completion guidelines.
- If an SAE has been reported via a paper form because the eCRF database has been locked, no further action is necessary.
- For fatal or life-threatening events, copies of hospital case reports, autopsy reports, and other documents are also to be submitted by e-mail or fax when requested and applicable. Transmission of such documents should occur without personal subject identification, maintaining the traceability of a document to the subject identifiers.
- Additional information may be requested to ensure the timely completion of accurate safety reports.
- Any medications necessary for treatment of the SAE must be recorded onto the concomitant medication section of the subject's CRF/eCRF and the event description section of the SAE form.

7.4. Gilead Reporting Requirements

Depending on relevant local legislation or regulations, including the applicable US FDA Code of Federal Regulations, the EU Clinical Trials Directive (2001/20/EC) and relevant updates, and other country-specific legislation or regulations, Gilead may be required to expedite to worldwide regulatory agencies reports of SAEs, serious adverse drug reactions (SADRs), or suspected unexpected serious adverse reactions (SUSARs). In accordance with the EU Clinical Trials Directive (2001/20/EC), Gilead or a specified designee will notify worldwide regulatory agencies and the relevant IEC in concerned Member States of applicable SUSARs as outlined in current regulations.

Assessment of expectedness for SAEs will be determined by Gilead using reference safety information specified in the investigator's brochure or relevant local label as applicable.

All investigators will receive a safety letter notifying them of relevant SUSAR reports associated with any study IMP. The investigator should notify the IRB or IEC of SUSAR reports as soon as is practical, where this is required by local regulatory agencies, and in accordance with the local institutional policy.

7.5. Toxicity Management

- All clinical and clinically significant laboratory toxicities will be managed according to uniform guidelines detailed in [Appendix 3](#).
- Grade 3 and 4 clinically significant laboratory abnormalities should be confirmed by repeat testing within 3 calendar days of receipt of results and before investigational medicinal product discontinuation, unless such a delay is not consistent with good medical practice.
- Clinical events and clinically significant laboratory abnormalities will be graded according to the Table for GSI Grading Scale for Severity of Adverse Events and Laboratory Abnormalities ([Appendix 4](#)).
- When restarting investigational medicinal product following resolution of the adverse event, the investigational medicinal product should be restarted at full dose or modified dose that is dependent upon discussion with the Gilead Sciences Medical Monitor.
- Any recurrence of the investigational medicinal product-related Grade 3 or 4 clinical or clinically significant laboratory adverse event following dose interruption mandates permanent discontinuation of investigational medicinal product.
- Administration of study drug may be discontinued due to a clinical or laboratory event. The Gilead Medical Monitor should be consulted prior to dose discontinuation of study drug unless the investigator believes that immediate action is warranted to ensure the continued safety of subject.
- Any questions regarding toxicity management should be directed to the Gilead Sciences Medical Monitor.

7.5.1. Grades 1 and 2 Laboratory Abnormality or Clinical Event

- Continue investigational medicinal product at the discretion of the investigator.

7.5.2. Grade 3 Laboratory Abnormality or Clinical Event

- For Grade 3 clinically significant laboratory abnormality or clinical event, investigational medicinal product may be continued if the event is considered to be unrelated to investigational medicinal product.
- For a Grade 3 clinical event, or clinically significant laboratory abnormality confirmed by repeat testing, that is considered to be related to investigational medicinal product, investigational medicinal product should be withheld until the toxicity returns to \leq Grade 2.
- If a laboratory abnormality recurs to \geq Grade 3 following rechallenge with investigational medicinal product and is considered related to investigational medicinal product, then investigational medicinal product should be permanently discontinued and the subject managed according to local practice. Recurrence of laboratory abnormalities considered unrelated to investigational medicinal product may not require permanent discontinuation.

7.5.3. Grade 4 Laboratory Abnormality or Clinical Event

- For a Grade 4 clinical event or clinically significant Grade 4 laboratory abnormality confirmed by repeat testing that is considered related to investigational medicinal product, investigational medicinal product should be permanently discontinued and the subject managed according to local practice. The subject should be followed as clinically indicated until the laboratory abnormality returns to baseline or is otherwise explained, whichever occurs first. A clinically significant Grade 4 laboratory abnormality that is not confirmed by repeat testing should be managed according to the algorithm for the new toxicity grade.
- Investigational medicinal product may be continued without dose interruption for a clinically non-significant Grade 4 laboratory abnormality (e.g., Grade 4 CK after strenuous exercise, or triglyceride elevation that is non-fasting or that can be medically managed) or a clinical event considered unrelated to investigational medicinal product.

7.5.4. Management of Bone Evaluation

As there is uncertainty surrounding the clinical significance and management of decreases in bone mineral density for chronic HBV-infected patients, Gilead recommends that any subject who has a DXA scan that demonstrates a decrease from baseline of $> 5\%$ in bone mineral density of the spine region or the hip region be followed per local medical practice at the discretion of the investigator.

7.5.5. On-Treatment ALT Flare and Post-Treatment Exacerbation of Hepatitis Management

On-Treatment ALT Flare is defined as:

- Confirmed (within 3 days of receipt of initial laboratory results) serum ALT $> 2 \times$ baseline value and $> 10 \times$ ULN, with or without associated symptoms

7.5.5.1. Management of ALT Flare in Subjects Receiving Study Medication

If laboratory results indicate elevation of ALT $> 2 \times$ baseline and $> 10 \times$ ULN, the following is recommended:

- Schedule the subject to return to the clinic as soon as possible (ideally within 3 days after initial laboratory results were drawn). During the visit, a clinical assessment of the subject will be performed. The assessment should include a physical examination and evaluation of the subject's mental status.
- Check the following laboratory parameters: serum ALT and AST, total bilirubin, INR, and serum albumin.
- If the ALT elevation is confirmed, the central clinical laboratory will conduct reflex testing for plasma HBV DNA, serology for HBV (HBsAg and HBsAb), HDV, HAV IgM, HCV, and HEV.

Based on the results of the confirmatory tests, the following treatment modifications are recommended:

Elevated Liver Enzymes, Normal or Stable Relative to Baseline Liver Function Tests

If ALT levels are elevated (i.e., $> 2 \times$ baseline and $> 10 \times$ ULN) with normal or stable total bilirubin and INR relative to baseline, the subject may remain on study medication and should be monitored weekly as long as ALT levels return to normal or baseline level.

During monitoring, if the ALT values remain persistently elevated, the investigator should discuss with the Gilead Medical Monitor whether the study drug should be discontinued.

For subjects with bridging fibrosis or cirrhosis, study drug discontinuation with treatment-free follow-up is to be avoided due to the potential risk of exacerbation of hepatitis in the setting of low hepatic reserve which could lead to decompensation. Subjects with bridging fibrosis or cirrhosis should be placed on commercially available HBV therapy following study drug discontinuation.

Elevated Liver Enzymes, Elevated Liver Function Tests

If ALT values are elevated (i.e., $> 2 \times$ baseline and $> 10 \times$ ULN), and total bilirubin is confirmed to be $2 \times$ baseline value, and INR is 0.5 above baseline, provided both are $> ULN$, the investigator should consider discontinuing study medication (upon discussion with the Gilead Medical Monitor, unless the safety of the subject is of immediate concern).

The subject should be monitored weekly as long as ALT, total bilirubin, and INR values remain elevated or above baseline values.

During monitoring, if the ALT values and the liver function tests remain persistently elevated, the investigator should discuss with the Gilead Medical Monitor whether the study drug should be discontinued.

For subjects with bridging fibrosis or cirrhosis, study drug discontinuation with treatment-free follow-up is to be avoided due to the potential risk of exacerbation of hepatitis in the setting of low hepatic reserve which could lead to decompensation. Subjects with bridging fibrosis or cirrhosis should be placed on commercially available HBV therapy following study drug discontinuation.

7.5.5.2. Management of Exacerbation of Hepatitis in Subjects Who Have Discontinued Study Medication

If laboratory results indicate (1) an ALT elevation $> 2 \times$ baseline and $> 10 \times$ ULN alone OR associated with (2) abnormal laboratory parameters suggestive of worsening hepatic function (total bilirubin $2 \times$ baseline, INR 0.5 above baseline, provided both are $> ULN$) and the subject is on no post-study therapy for HBV, the following is recommended:

- Schedule the subject to return to the clinic as soon as possible (ideally no later than 3 days after the initial laboratory values were drawn). During the visit, perform a clinical assessment of the subject.
- Check the following laboratory parameters: serum ALT and AST, total bilirubin, INR, creatinine, sodium, and albumin.
- If the ALT elevation is confirmed, the central clinical laboratory will conduct reflex testing for plasma HBV DNA, serology for HBV (HBsAg and HBsAb), HDV, HAV IgM, HCV and HEV. If Plasma HBV DNA is increasing, the investigator should consider immediate initiation of approved therapy.
- The subject should be followed until laboratory parameters (ALT, total bilirubin, INR) return to normal or baseline up to a maximum of 6 months after the initial occurrence of the event.

7.5.6. Management of Potential Nephrotoxicity

For subjects with moderate or severe renal impairment (Part A, Cohort 1), and subjects with hepatic impairment (Part B), eGFR_{CG} will be followed post-baseline during the study.

eGFR_{CG} is calculated by:

$$\frac{(140 - \text{age in years}) (\text{actual body weight [kg]})}{(72) (\text{serum creatinine [mg/dL]})}$$

(Note: multiply estimated rate by 0.85 for women)

Any subject with a post baseline eGFR_{CG} < 15 mL/min must have serum creatinine measured again within 3 calendar days of receipt of results. At the time of this repeat serum creatinine assessment, serum Cystatin C will also be measured and the eGFR by CKD-EPI (cystatin C) will be calculated and compared with the baseline measurement. Any subject who has an eGFR_{CG} < 15 mL/min who also experiences > 20% reduction in eGFR by CKD-EPI (cystatin C) from baseline or any subject who has other clinical and/or laboratory evidence of acute renal failure will be discussed with the Medical Monitor and may require discontinuation from study drugs.

CKD-EPI (cystatin C) formula adjusted for age and sex:

$$\text{eGFR (mL/min/1.73m}^2\text{)} = 133 \times \min(\text{Scys}/0.8, 1)^{-0.499} \times \max(\text{Scys}/0.8, 1)^{-1.328} \times 0.996^{\text{Age}}$$

[× 0.932 if female],

where Scys is serum cystatin C (mg/L), min (Scys/0.8,1) indicates the minimum of Scys/0.8 or 1, and max (Scys/0.8,1) indicates the maximum of Scys/0.8 or 1.

If the eGFR_{CG} is confirmed to be < 15 ml/min and hemodialysis is to be initiated, the subject can remain on study after discussion with the Medical Monitor. However, any subject with eGFR < 15 mL/min who does not initiate hemodialysis, or those who initiate other forms of renal support (e.g. peritoneal dialysis) will be required to permanently discontinue study drug.

All subjects with moderate or severe renal impairment with a change from baseline serum creatinine of ≥ 0.4 mg/dL must have serum creatinine repeated, with a concurrent urinalysis and urine chemistry, within 2 weeks of receipt of results. If a subject has a confirmed change from baseline serum creatinine of ≥ 0.4 mg/dL, the Medical Monitor should be notified and a consultation with a nephrologist should be obtained.

All subjects with moderate or severe renal impairment with negative or trace proteinuria at baseline that develop ≥ 1+ proteinuria on urinalysis are recommended to have a urinalysis repeated, with a concurrent urinalysis and urine chemistry, within 2 weeks of receipt of results. Any subject with ≥ 1+ proteinuria at baseline who develops a ≥ 1+ change from baseline should follow this same procedure. Upon confirmation of new proteinuria, subjects will be asked to return to the clinic for a scheduled or unscheduled follow up visit for evaluation. It is recommended that the Investigator contact the Gilead Medical Monitor to discuss if further consultation with a nephrologist is clinically warranted.

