8.1.3. Secondary Endpoint

[figure not shown]
The Secondary safety endpoints are:

[figure not shown]
- Incidence of graded adverse events and graded laboratory abnormalities at Week 48 and 96
- Change from baseline in eGFR_{CG} at Weeks 24, 48, and 96 in subjects with moderate or severe renal impairment and hepatically impaired subjects
- Percent change from baseline in hip and spine bone mineral density (BMD) at Weeks 24, 48, and 96

The Secondary efficacy endpoints are:

- Proportion of subjects achieving virologic response (plasma HBV DNA < 20 IU/mL) at Weeks 48 and 96
- Proportion of subjects with plasma HBV DNA < 20 IU/mL and target detected/not detected (i.e. < LLOD) at Weeks 24, 48, and 96
- Proportion of subjects with serological response (loss of HBsAg and seroconversion to anti-HBs, loss of HBeAg and seroconversion to anti-HBe in HBeAg-positive subjects) at Weeks 24, 48, and 96
- Proportion of subjects with biochemical response (normal ALT and normalized ALT) at Weeks 24, 48, and 96
- Change in fibrosis as assessed by FibroTest[®] at Weeks 24, 48, and 96
- Change from baseline in CPT score ([Appendix 7](#)) and MELD score at Weeks 24, 48, and 96 in hepatically impaired subjects

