8.8. Biomarker Analysis

Selected renal biomarkers, including retinol binding protein, beta-2 microglobulin, will be summarized for Part A, Cohort 1 (moderate or severe renal impairment) and Part B (moderate or severe hepatic impairment) by visit using descriptive statistics.

Selected bone biomarkers, including C-type collagen sequence (CTX) and procollagen type 1 N-terminal propeptide (P1NP), will be summarized by visit using descriptive statistics.

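### The mandatory repeat after a creatinine rise of 0.4 mg/dL or more (Protocol 7.5.6) does not name Part B, and on any reading it leaves some Part B subjects without one

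*Protocol*

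**What the plan says.** Section 7.5.6 begins with the two groups whose eGFR_CG is followed on study: "For subjects with moderate or severe renal impairment (Part A, Cohort 1), and subjects with hepatic impairment (Part B"). It then sets rules of different scope and force.

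- **eGFR_CG below 15 mL/min.** Any subject must have creatinine measured again within 3 calendar days of the result. Footnote n of Appendix 2 repeats this rule.
- **Acute renal failure clause.** "any subject who has other clinical and/or laboratory evidence of acute renal failure will be discussed with the Medical Monitor". It has no numeric threshold and asks for a discussion, not a repeat test.
- **Creatinine rise.** "All subjects with moderate or severe renal impairment with a change from baseline serum creatinine of" 0.4 mg/dL or more must have creatinine repeated, with urinalysis and urine chemistry, within 2 weeks of the result.
- **Confirmed rise.** The next sentence is wider: "If a subject has a confirmed change from baseline serum creatinine of" that size, the Medical Monitor should be told and a nephrologist consulted.
- **Proteinuria.** The first sentence is a recommendation for the narrower group: "All subjects with moderate or severe renal impairment with negative or trace proteinuria at baseline". The second covers any subject already at 1+ or more, for whom a further 1+ "change from baseline should follow this same procedure".

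Outside 7.5.6, Section 7.5 asks for a repeat within 3 days for clinically significant Grade 3 or 4 abnormalities (a *should*). In Appendix 4, creatinine reaches Grade 3 above 3.00 mg/dL. Section 7.5.1, on Grades 1 and 2, speaks only of continuing the drug.

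**The concern.** The section monitors renal function in two groups but attaches its most sensitive mandatory follow-up to a phrase that, a few lines earlier, it tied to only one of them. Part B has its own renal interest. Section 1.3 says renal complications are more common in decompensated liver disease. Section 2 makes the renal effect in hepatically impaired subjects a secondary objective. Section 1.4 counts possible better renal safety among the benefits of TAF in CPT Class B and C.

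What is at stake is timing. A rise will be seen, because creatinine and eGFR_CG are measured at every visit. But notification and nephrology referral start from a *confirmed* rise, so where no repeat is required, both can wait for the next scheduled value. Two sites can also read the sentence differently and manage the same Part B subject differently.

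**Working it through.** The plan gives no figure to reproduce. The check has three parts: what the phrase means, what each meaning covers, and how long a Part B subject may wait.

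**1. Meaning of the phrase.** The creatinine sentence does not repeat the Cohort 1 tag, so three readings are possible.

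- *Cohort label.* Section 7.5.6 itself glosses the phrase as Part A Cohort 1. Section 8.8 does the same, setting "Part A, Cohort 1 (moderate or severe renal impairment) and Part B (moderate or severe hepatic impairment") side by side, and so does footnote t of Appendix 2. Section 8.1.3 also separates the groups: "at Weeks 24, 48, and 96 in subjects with moderate or severe renal impairment and hepatically impaired subjects". Where 7.5.6 means everyone, it says any subject.
- *Category judged at baseline.* Section 4.2 defines moderate impairment as eGFR_CG 30 to 59 mL/min and severe as 15 to below 30. Part B requires only 30 or more, with no upper limit, so some Part B subjects could enter as moderate.
- *Category judged at the current value.* The same cut-offs, applied after the rise.

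**2. Coverage.** The formula is the protocol's: eGFR_CG = (140 − age) × weight / (72 × creatinine), times 0.85 for women. The creatinine values, ages and weights below are assumptions. Creatinine goes from 0.8 to 1.6 mg/dL, a rise of 0.8 and so twice the threshold. At 1.6 it is Grade 1.

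| Assumed man | Before | After | Cohort label | Baseline | Current |
|---|---|---|---|---|---|
| 40 y, 80 kg | 8000/57.6 = 138.9 | 69.4 | no | no | no |
| 60 y, 70 kg | 5600/57.6 = 97.2 | 48.6 | no | no | yes |
| 80 y, 50 kg | 3000/57.6 = 52.1 | 26.0 | no | yes | yes |

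The rule for eGFR_CG below 15 does not help here. Doubling creatinine halves eGFR_CG, and from the entry floor of 30 that gives exactly 15.0, which is not below 15.

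**3. eGFR_CG loss at the first numeric repeat trigger.** At fixed age and weight, eGFR_CG × creatinine is constant. Assume 90 × 0.8 = 72. For baseline creatinine b:

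- Part B named: trigger at b + 0.4, loss = 1 − b/(b + 0.4).
- Cohort label: first trigger is Grade 3, loss = 1 − b/3.0. The rule for eGFR_CG below 15 would need creatinine above 72/15 = 4.8, so it comes later.
- Baseline category: all four baselines are 60 or above, so the result is the same as for the cohort label.
- Current category: trigger at the larger of 72/59 = 1.22 and b + 0.4.

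| b (mg/dL) | eGFR_CG | Part B named | Cohort label or baseline | Current |
|---|---|---|---|---|
| 0.6 | 120 | 40% | 80% | 51% |
| 0.8 | 90 | 33% | 73% | 34% |
| 1.0 | 72 | 29% | 67% | 29% |
| 1.2 | 60 | 25% | 60% | 25% |

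The 60% to 80% column treats the Grade 3 value as clinically significant and assumes no further rule in Appendix 3.

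**4. Waiting time.** Visits are at Weeks 4, 8, 12, 24, 36, 48, 60, 72 and 96, so the nominal gaps from Week 4 on are 4, 4, 12, 12, 12, 12, 12 and 24 weeks. A rise first seen at Week 4 or 8 is rechecked on schedule after 4 weeks; one seen at Weeks 12 to 60 after 12 weeks; one seen at Week 72 after 24 weeks. The mandated repeat is due within 2 weeks of the result.

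**The case against.** The strongest reply is that this is a wording point with a workable reading. The category is defined by eGFR_CG, the sentence omits the cohort tag, and read at the current value it covers many Part B subjects once creatinine has risen. For assumed baselines of 0.8 mg/dL and above, naming Part B then gains at most one percentage point (33% against 34%). That stands, but only for that reading, and it still leaves out subjects with high baseline eGFR_CG.

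The phrase standing alone is also weak evidence of a deliberate exclusion. Section 8.6.2 uses it alone for the eGFR_CG summary, although Section 8.1.3 assigns that endpoint to hepatically impaired subjects too. This stands. The documents do not show intent, and a tighter rule for those enrolled for renal impairment, with judgement for the rest, would be a defensible choice if stated.

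There are other safeguards. Unscheduled visits can be requested (6.5) and the drug can be stopped for toxicity (6.6). Abnormalities that need intervention, interrupt the drug or come with symptoms are recorded as adverse events (7.1.3) and followed until resolved or stable where possible (7.3). Same-day data entry supports central safety monitoring (9.1.6). The confirmed-rise sentence may already reach Part B. Together these make a long unattended interval a worst case, not the expected course. None of them requires the repeat.

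Finally, Section 7.5 refers clinically significant laboratory toxicities to Appendix 3, whose content is missing from the text available for this review. A rule there could close the gap and should be checked first.

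**Conclusion.** The point holds as a gap in the scope of one mandatory safety rule. Part B coverage is none on the cohort-label reading, which is the best supported. It is limited to entrants at 30 to 59 mL/min on the baseline reading, and to subjects at 59 mL/min or below after the rise on the current-value reading. On all three, some Part B subjects with a rise of 0.4 mg/dL or more have no visible mandated repeat, and the next scheduled creatinine is 4 to 24 weeks away.

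A reader might infer more than this, and the documents do not support it:

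- *That Part B has no renal safety net.* Labs at every visit, the rule for eGFR_CG below 15 and the acute renal failure clause all apply to it.
- *That any doubling from 0.8 to 1.6 mg/dL escapes the rule.* On the current-value reading the 60-year-old above is covered, and so is the 80-year-old.
- *That the exclusion was intended, or that a given number of events will be missed.* Nothing states intent, and no event rate for TAF in Part B is given.

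The percentages rest on assumed baselines with fixed age and weight, and the conclusion rests on Appendix 3 adding no equivalent rule. No endpoint or analysis is affected. This is a cheap patient-safety improvement of low to moderate severity.

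**What to change.** In the creatinine-rise sentence of Section 7.5.6, replace the description of who is covered with: *All subjects in Part A Cohort 1 and Part B*. Keep the threshold, tests and two-week limit as they are. Name the same two groups in the first proteinuria sentence for consistency. If Part B is meant to stay outside the repeat, say so and state how a creatinine rise there is to be handled. Thresholds and clinical action remain for the sponsor to set.

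The cost is one phrase in each of two sentences, plus a few reflex creatinine and urine tests and possible nephrology consultations among about 30 subjects. The scheduled laboratory visits stay the same.
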